2.2 Secondary objectives

- To investigate whether switching patients to DTG/RPV FDC is associated with improvement of lipid profile, patient satisfaction, quality of life and potential for drug-drug interactions, investigated over time through 96 weeks with evaluation (and comparison to control arm) at week 24, 48 and 96.
- To evaluate DTG & RPV trough concentrations
- Changes in cell associated virus (using Peripheral Blood Monoclonal Cell (PBMC) analysis)

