2.3.2 Secondary endpoints/outcomes

- Proportion of participants with plasma HIV-1 RNA <50 c/mL at week 24, 48 and 96.
- Changes in laboratory parameter from baseline.
- Changes in renal markers, bone markers, and fasting lipids from baseline at week 24, 48 and 96.

CONFIDENTIAL

- Resistant outcomes in failures (descriptive analysis) and baseline factors associated with failure i.e. treatment emergent mutations (NRTI, NNRTI, PI and II regions) as compared with previous resistance tests.
- Changes in QoL and patient satisfaction from baseline.
- Number of participants with adverse events (AEs), severity of AEs, and treatment discontinuations due to AEs.
- Number of potential DDIs avoided (This will be measured by comparing the drug interaction outcomes between antiretroviral therapy and co-medications before and after the switch by using the www.hiv-druginteractions.org/ website (within the same study arm and between study arms). The grading will be done by looking at how many interactions graded amber or red will be graded green after the switch. For example, if a patient on atorvastatin as a co-medication and on two NRTIs and darunavir/cobicistat he would score “one amber and two green” and when switched to rilpivirine/dolutegravir, he would score “all green”, showing the latter regimen is more favourable in terms of drug-drug interactions).
- Virological suppression (<200 copies/ml HIV RNA) at week 24, 48, 96 in individuals with previous NNRTIs virological failure and/or baseline transmitted resistance with the k103N resistance mutation, switching to DTG/RPV FDV. Analysed in line with FDA Snapshot method.
- Pre-dose plasma concentrations of DTG and RPV at week 4 (experimental arm only), 48 (experimental arm only) & 96. Plus pre/post-dose (as appropriate) at early termination visit and /or in the event of virological failure (see section 6.12) a post dose sample will be taken within 20-28 hours.
- Changes in cell associated virus using PBMC Illumina MiSeq sequencing at week 48 and week 96.

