25. Screening blood result with any grade 3/4 toxicity according to Division of AIDS (DAIDS) grading scale, except: asymptomatic grade 3 glucose, amylase or lipid elevation, asymptomatic grade 4 triglyceride elevation (re-test allowed) or unconjugated hyperbilirubinaemia due to atazanavir exposure.
26. Any condition (including illicit drug use or alcohol abuse) or laboratory results which, in the investigator's opinion, interfere with assessments or completion of the trial.
27. Women planning pregnancy or who are pregnant or breast feeding. (NB: See section 6.12 Withdrawal Criteria for guidance if pregnancy does occur).
28. Females of childbearing potential and males must be willing to use a highly effective (acceptable effective contraceptive measures are only acceptable for IMP's with unlikely human teratogenicity /

CONFIDENTIAL

fetotoxicity in early pregnancy) method of contraception (hormonal method of birth control; true abstinence). Contraceptive methods that can achieve a failure rate of less than 1% per year when used consistently and correctly are considered as highly effective birth control methods (see Appendix 4).

Such methods include:

- combined (estrogen and progestogen containing) hormonal contraception associated with inhibition of ovulation:
 - oral
 - intravaginal
 - transdermal
- progesteron-only hormonal contraception associated with inhibition of ovulation
 - oral
 - injectable
 - implantable
- Intrauterine device (IUD)
- Intrauterine hormone-releasing system (IUS)
- bilateral tubal occlusion
- vasectomised partner
- true sexual abstinence

(NB: See section 6.12 Withdrawal Criteria for guidance if pregnancy does occur).

29. Hypersensitivity to the active substances or to any of the excipients listed below:

List of excipients

Tablet core

- Mannitol (E421)
- Magnesium stearate
- Microcrystalline cellulose
- Povidone (K29/32)
- Sodium starch glycolate
- Sodium stearyl fumarate
- Lactose monohydrate
- Croscarmellose sodium
- Povidone (K30)
- Polysorbate 20
- Silicified microcrystalline cellulose

Tablet coating

- Polyvinyl alcohol- part hydrolysed
- Titanium dioxide (E171)
- Macrogol
- Talc
- Iron oxide yellow (E172)
- Iron oxide red (E172)

CONFIDENTIAL

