7.9 Prior Concomitant Therapy

All medications (prescriptions or over-the-counter medications, herbal and naturopathic products) continued at the start of the treatment or started during the treatment must be documented (dose, frequency, stop and start dates). Unnecessary changes or additions to any concomitant medication should be avoided.

Warnings and precautions regarding contraindicated concomitant medications, AE and drug interactions can be found above or within reference safety information.

NOTE! Caution must also be applied when patients take medications that inhibit CYP3A as this may lead to excessive exposure of rilpivirine.

Any medications excluded in the Exclusion criteria will not be permitted in this study. However, if there is a clinical need for the use of any of these medications then the participant may need to be discontinued from the study. If this is the case, then the investigator should discuss with the CI or Sponsor trials team, but the final decision remains that of the site investigator.

All concomitant medication information will be captured in the participant's Case Report Forms.

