3.2.2 Secondary endpoints/outcomes

Secondary endpoints will include secondary efficacy endpoints, secondary safety endpoints, pharmacological endpoints, and secondary endpoints regarding patient related outcomes.

Secondary efficacy endpoints:

- (a) Proportion of participants with virological failure (2 consecutive viral loads > 50 copies at least 2 weeks apart or a viral load > 50 copies/mL followed by a discontinuation of the study or the study treatment), investigated over 96 weeks.
- (b) Incidence of genotypic resistance in case of confirmed HIV RNA > 50 copies/mL and baseline factors associated with failure i.e. treatment emergent mutations (NRTI, NNRTI, PI and II regions) as compared with previous resistance tests.
- (c) Proportion of participants with plasma HIV-1 RNA < 50 c/mL at week 24, 48 and 96.
- (d) Proportion of participants with virological suppression (< 200 copies/ml HIV RNA) at week 24, 48, 96
- (e) Changes from baseline in cell associated virus using PBMC Illumina MiSeq sequencing at week 48 and week 96.
- (f) Changes from baseline in CD4, CD8 and CD4/CD8 ratio over 96 weeks with evaluation at week 24, 48 & 96.

Secondary safety endpoints:

- (g) Number and percentage of participants with adverse events (AEs), severity of AEs, and treatment discontinuations due to AEs.
- (h) Changes from baseline in laboratory parameter at week 24, 48 and 96.
- (i) Changes from baseline in renal markers, bone markers, and fasting lipids at week 24, 48 and 96.

Secondary endpoints regarding pharmacological outcomes:

- (j) Pre-dose plasma concentrations of DTG and RPV at week 4 (experimental arm only), 48 (experimental arm only) & 96. Plus pre/post-dose (as appropriate) at early termination visit and /or in the event of virological failure a post dose sample will be taken within 20-28 hours.

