6.5 Missing data

In the primary efficacy analysis (FDA Snapshot), participants with missing data at analysis time points will be considered as having lost undetectable plasma HIV-1 RNA levels. The analyses of overall patient disposition will show the number of patients who did not attend each protocol-defined visit.

For all continuous efficacy and safety variables, we will use, in the mITT population, the LOCF (last observation carried forward) approach to deal with missing data. We will also use mixed model as a sensitivity analysis.

For patients reported outcomes, we will use multiple imputation approach to fill in missing data.

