(h) Changes from baseline in laboratory parameters at week 24, 48 and 96.

The evolution of haematology parameters (including haemoglobin, white cell count and differential, platelets) and biochemistry parameters (including sodium, glucose, ALT, AST, and total bilirubin) according to the treatment group will be described by boxplots for each treatment group at baseline, week 24, 48 and 96. The changes from baseline will be compared between the two treatment groups

using mixed models for repeated measures with random intercept and unstructured covariance matrix adjusted for baseline value. The model will include treatment group, time and interaction between treatment group and time, and baseline value. Time will be considered as categorical variables. Data will be also summarised in tables by mean and standard error.

If the residual of the mixed model is not normally distributed and therefore does not allow the use of parametric test, the non-parametric Mann-Whitney-Wilcoxon test will be used to compare the changes from baseline to week 24, 48 and 96 between the two treatment groups.

(i) Changes from baseline in renal markers, bone markers, and fasting lipids at week 24, 48 and 96.

The evolution of renal markers (including blood creatinine, blood creatinine clearance (eGFR), urine creatinine, urine protein, urine protein/creatinine ratio, blood albumin, urine albumin, urine albumin/creatinine ratio, urine beta 2 microglobulin, urine creatinine clearance (eGFR), potassium, blood phosphate, urine phosphate), bone markers (including ALP) and lipids fasting parameters (including total cholesterol, HDL, LDL, triglycerides) according to the treatment group will be described by boxplots for each treatment group at baseline, week 24, 48 and 96.

The changes from baseline will be compared between the two treatment groups using mixed models for repeated measures with random intercept and unstructured covariance matrix adjusted for baseline value. The model will include treatment group, time and interaction between treatment group and time, and baseline value. Time will be considered as categorical variables. Data will be also summarised in tables by mean and standard error.

If the residual of the mixed model is not normally distributed and therefore does not allow the use of parametric test, the non-parametric Mann-Whitney-Wilcoxon test will be used to compare the changes from baseline to week 24, 48 and 96 between the two treatment groups.

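### The lipid comparison makes no use of the recorded lipid-lowering drug data, so it cannot separate the effect of the antiretroviral switch from lipid treatment that differs by arm

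*Protocol*

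**What the plan says.** - **Objective.** Protocol 2.2 opens with "To investigate whether switching patients to DTG/RPV FDC is associated with improvement of lipid profile" and asks for evaluation against the control arm at weeks 24, 48 and 96.
- **Endpoint.** SAP 3.2.2(i), among the secondary safety endpoints: "Changes from baseline in renal markers, bone markers, and fasting lipids at week 24, 48 and 96".
- **Model.** SAP section 9(i), on change from baseline: "The model will include treatment group, time and interaction between treatment group and time, and baseline value". If the residuals are not normal, "the non-parametric Mann-Whitney-Wilcoxon test will be used to compare the changes from baseline to week 24, 48 and 96 between the two treatment groups". Neither method has a term for lipid-lowering drugs.
- **Missing values.** For continuous efficacy and safety variables, SAP 6.5 uses "the LOCF (last observation carried forward) approach to deal with missing data", with a mixed model as sensitivity analysis. It has no rule for values observed after a co-medication change.
- **Drug data.** Protocol 7.9 requires that medications "continued at the start of the treatment or started during the treatment must be documented", including doses and dates. The same section discourages co-medication changes that are not needed, without naming lipid-lowering drugs. SAP 7.5 describes drugs that are ongoing or started, but does not mention stops or dose changes. Lipid-lowering drugs appear neither in the baseline list of SAP 7.3 nor in the covariate list of SAP 6.4.2, which in any case serves the virological outcome.
- **Setting.** The trial is open-label (Protocol 6.6.1). Protocol 2.3.2 builds its drug-interaction example on a statin ("if a patient on atorvastatin as a co-medication"). Exclusion criterion 25 does not exclude "asymptomatic grade 3 glucose, amylase or lipid elevation, asymptomatic grade 4 triglyceride elevation".

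**The concern.** The objective asks whether leaving the old regimen improves lipids. Fasting lipids are measured at every on-treatment clinic visit (Protocol Appendix 1) and analysed at local laboratories (Protocol 6.18). Sites therefore know both the arm and the result, and lipid treatment can respond to either. Until week 48 the arms are on different regimens, so the pattern of starts, stops and dose changes may differ between them.

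More starts among controls, or more stops among switchers, would shrink the observed lipid difference. More starts or dose increases among switchers would enlarge it. The planned model credits the net result to arm, and nothing planned beside it lets a reader see how much comes from lipid drugs. At stake is the interpretation of the first-named item in the first secondary objective, not the primary endpoint.

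**Working it through.** **Reading the plan.** Setting the sections side by side, the drug data needed are collected (Protocol 7.9, with a medication check at each clinic visit in Appendix 1). They enter no lipid model, fallback test, missing-data rule or sensitivity analysis (SAP 6.5, 7.5 and 9(i)).

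**No plan figure to reproduce.** The documents give no SD, effect size or power for lipids, and no rate of lipid-drug change. What follows is illustration only.

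**Inputs from the documents.** 100 and 50 participants (Protocol 9.1), and 15% expected loss to follow-up (Protocol 6.12). A two-sided 0.05 level is stated for secondary efficacy outcomes in SAP 8.2. SAP section 9 states none for lipids, so 0.05 is assumed.

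**Assumptions.** Drug effect L = 1.0 to 1.5 SD of lipid change. Net imbalance in drug changes between arms q = 5% to 20%. Drug effects add to the antiretroviral effect.

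**Detectable difference, in SD units.** SE = sqrt(1/100 + 1/50) = 0.173. With 80% power this is (1.96 + 0.84) x 0.173 = 0.485 SD. After 15% loss (85 and 42.5), it is 0.526 SD.

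**Shift.** Observed difference = true difference - qL when the imbalance works against the switch arm, and + qL when it works in its favour. Power = Phi(observed/SE - 1.96). For a true benefit of 0.485 SD, the first value in each cell is for L = 1.0 and the second for L = 1.5:

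| q | Observed, imbalance against switch | Power | Observed, imbalance favouring switch |
|---|---|---|---|
| 0 | 0.485 | 80% | 0.485 |
| 5% | 0.435 to 0.410 | 71% to 66% | 0.535 to 0.560 |
| 10% | 0.385 to 0.335 | 60% to 49% | 0.585 to 0.635 |
| 20% | 0.285 to 0.185 | 38% to 19% | 0.685 to 0.785 |

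If the switch itself had no lipid effect, a 10% imbalance in its favour would give an observed 0.10 to 0.15 SD. The chance of a significant result favouring the switch would then rise from 2.5% to between 8.3% and 13.7%.

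**The same in LDL units, all assumed.** SD of change 0.8 mmol/L gives SE = 0.8 x 0.173 = 0.139. A 1.0 mmol/L drug effect with a 10% excess of starts in controls shifts the difference by 0.10 mmol/L, or 0.10/0.139 = 0.7 SE. For a true 0.4 mmol/L benefit, power goes from 82% to 58%. With a shift of 0.05 x 0.8 = 0.04 it is 74%, and with 0.15 x 1.5 = 0.225 it is 24%. The width of that range shows that no particular size is established.

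**The case against.** **The planned estimate is legitimate.** Using all observed values compares lipids under the switch strategy with lipids under continued therapy, later co-medication included. That is a treatment-policy answer to the objective as worded. This stands, and it is why the as-observed analysis should remain the main one.

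**A reader might infer that a real benefit would mostly be masked.** The documents do not support a favoured direction. In the statin example of Protocol 2.3.2 the interaction grade disappears after the switch, which could equally ease starts or dose increases in the switch arm and enlarge the apparent benefit.

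**A reader might infer that drug use at baseline biases the comparison.** It does not do so systematically: allocation is randomised and the model adjusts for the baseline lipid value. Adding baseline use would help precision and guard against chance imbalance with 50 controls. Exclusion criterion 25 shows only that people with raised lipids may enter, not how many will.

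**Exposure may be modest.** Protocol 7.9 discourages unnecessary co-medication changes in both arms. That lowers the likely imbalance, but it neither rules out needed changes nor supplies an analysis rule. The contrast between regimens also applies mainly to weeks 24 and 48, because the deferred arm switches at week 48.

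**This is a pilot with no formal sample size calculation and no power claim for lipids.** That is so, and the power figures above are not a criticism of the sample size.

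**Conclusion.** The point holds as a cheap improvement to a secondary endpoint. SAP section 9(i) uses none of the recorded lipid-lowering drug data. Its estimate therefore cannot separate the effect of the antiretroviral switch from lipid treatment that differs by arm up to week 48. The planned estimate is not an error: it is a valid treatment-policy comparison with nothing beside it to aid interpretation.

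Direction and size are both unknown. The conclusion rests on the open-label design, on sites seeing the lipid results and on needed drug changes being allowed, all of which the documents show. That changes will in fact differ by arm is a possibility, not something the documents establish. The illustrative figures depend wholly on the assumed SD, drug effect and imbalance.

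**What to change.** In SAP section 9(i), for total cholesterol, HDL, LDL and triglycerides:

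1. Add baseline use of a lipid-lowering drug (yes/no) as a covariate, stating that its purpose is precision and protection against chance imbalance, not removal of bias.
2. Keep the as-observed analysis as the main one. Pre-specify a supplementary mixed-model analysis in which values after the first start, stop or dose change of a lipid-lowering drug are set to missing. State that the carry-forward rule in SAP 6.5 does not apply to those values, and that the analysis assumes they are missing at random.
3. Tabulate starts, stops and dose changes of lipid-lowering drugs by arm to weeks 24 and 48.

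**Cost.** SAP wording and a derivation from concomitant-medication data already collected, with no change to trial conduct. Analysis 2 uses fewer values, and a participant whose drug changes early may contribute no usable post-baseline value at the analysed visits. With 50 controls and 15% loss expected, that matters. Its assumption cannot be tested, and drug changes may themselves depend on arm and lipid level. It should therefore be reported as supportive only.

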2.3 Outcome measures/endpoints

2.3.1 Primary endpoint/outcome

- Virological suppression (<50 copies/ml HIV RNA) at week 48 in individuals with previous NNRTIs virological failure and/or baseline transmitted resistance with the K103N resistance mutation, switching to DTG/RPV FDC. Analysed with FDA snapshot.
- Virological failure will be 2 consecutive viral loads >50 copies at least 2 weeks apart, investigated over 48 weeks.

2.3.2 Secondary endpoints/outcomes

- Proportion of participants with plasma HIV-1 RNA <50 c/mL at week 24, 48 and 96.
- Changes in laboratory parameter from baseline.
- Changes in renal markers, bone markers, and fasting lipids from baseline at week 24, 48 and 96.

CONFIDENTIAL

- Resistant outcomes in failures (descriptive analysis) and baseline factors associated with failure i.e. treatment emergent mutations (NRTI, NNRTI, PI and II regions) as compared with previous resistance tests.
- Changes in QoL and patient satisfaction from baseline.
- Number of participants with adverse events (AEs), severity of AEs, and treatment discontinuations due to AEs.
- Number of potential DDIs avoided (This will be measured by comparing the drug interaction outcomes between antiretroviral therapy and co-medications before and after the switch by using the www.hiv-druginteractions.org/ website (within the same study arm and between study arms). The grading will be done by looking at how many interactions graded amber or red will be graded green after the switch. For example, if a patient on atorvastatin as a co-medication and on two NRTIs and darunavir/cobicistat he would score “one amber and two green” and when switched to rilpivirine/dolutegravir, he would score “all green”, showing the latter regimen is more favourable in terms of drug-drug interactions).
- Virological suppression (<200 copies/ml HIV RNA) at week 24, 48, 96 in individuals with previous NNRTIs virological failure and/or baseline transmitted resistance with the k103N resistance mutation, switching to DTG/RPV FDV. Analysed in line with FDA Snapshot method.
- Pre-dose plasma concentrations of DTG and RPV at week 4 (experimental arm only), 48 (experimental arm only) & 96. Plus pre/post-dose (as appropriate) at early termination visit and /or in the event of virological failure (see section 6.12) a post dose sample will be taken within 20-28 hours.
- Changes in cell associated virus using PBMC Illumina MiSeq sequencing at week 48 and week 96.

2.4 Exploratory endpoints/outcomes

- Changes in HsCRP over 96 weeks with evaluation at week 24, 48 & 96.
- Changes in CD4/CD8 over 96 weeks with evaluation at week 24, 48 & 96.

CONFIDENTIAL

3 TRIAL DESIGN

Open-label, randomised, 2 arm, multicentre trial over 96 weeks with early or delayed switch from an ARV regimen containing a boosted PI (and/or other antiretroviral combinations) to Dolutegravir (DTG) & Rilpivirine (RPV) combination therapy in patients with a history of virological failure with NNRTIs or baseline drug transmitted resistance and having developed a K103N mutation.

Patients will be randomised to switch at baseline or at 48 weeks.

Study visits will take place at screening, baseline, weeks 4, 12, 24, 48, 52, 72, 96, and either a follow-up visit (30 days (+/- 7 days) after week 96 visit) or an early termination visit. An optional visit at week 60 may be performed for subjects on the control arm (3 months after therapeutic modification) as required per national guidelines

Routine investigations will include viral load, CD4 & CD8, haematology (including haemoglobin, white cell count and differential, platelets), biochemistry (including sodium, potassium, creatinine, albumin, glucose, ALT, AST, ALP, total bilirubin, total cholesterol, HDL, LDL, triglycerides), PK, PBMC, quality of life questionnaires (EuroQoL), patient satisfaction questionnaire, Pittsburgh sleep questionnaire, DDI assessment & urine sample (for haematuria, proteinuria, glycosuria, leukocytes) for full list of investigations please see appendix 1.

CONFIDENTIAL

3.1 Study Schema

Control Arm

Experimental Arm

Figure 1.0

4 STUDY SETTING

This study will be conducted within the NEAT ID network and include sites in 7 countries that have an excellent track record in clinical research. A full feasibility assessment will be undertaken for all potential sites. A Trial Management Team will facilitate the project. See section 9 & 12 for details of DSMB composition and responsibilities.

The sponsor will perform site visits to assess protocol issues, consent, project management, data quality, drug dispensing, and trial management quality performance.

CONFIDENTIAL

